16.3.10 TREATMENT RESPONSE: REDUCTION IN THE WOMAC LK3.1 OA INDEX (PHYSICAL FUNCTION)

The number and percentage of subjects with reduction in the WOMAC physical function score of $\geq 30\%$, $\geq 50\%$, $\geq 70\%$, and $\geq 90\%$ at Weeks 1, 2, 4, 8, and 12 (visits 4, 5, 6, 7, and 8) from baseline will be summarized by treatment groups.

The responders are defined as subjects with a reduction in the WOMAC physical function score of $\geq 30\%$, $\geq 50\%$, $\geq 70\%$, and $\geq 90\%$, and non-responders are defined as subjects with a reduction in the WOMAC physical function score of $<30\%$, $<50\%$, $<70\%$, and $<90\%$, respectively. Treatment comparisons will be made using a logit model with treatment effect as the only term in the model analyzing the proportion of WOMAC physical function score responders. For each comparison, an estimate of the odds ratio, corresponding Wald 95% CI, and p-value will be presented.

16.3.11 TREATMENT RESPONSE: REDUCTION IN THE WOMAC LK3.1 OA INDEX (STIFFNESS)

[figure not shown]
The number and percentage of subjects with reduction in the WOMAC stiffness score of $\geq 30\%$, $\geq 50\%$, $\geq 70\%$, and $\geq 90\%$ at Weeks 1, 2, 4, 8, and 12 (visit 4, 5, 6, 7, and 8) from baseline will be summarized in a table by treatment groups.

The responders are defined as subjects with a reduction in the WOMAC stiffness score of $\geq 30\%$, $\geq 50\%$, $\geq 70\%$, and $\geq 90\%$, and non-responders are defined as subjects with a reduction in the WOMAC stiffness score of $<30\%$, $<50\%$, $<70\%$, and $<90\%$, respectively. Treatment comparisons will be made using a logit model with treatment effect as the only term in the model analyzing the proportion of WOMAC stiffness score responders. For each comparison, an estimate of the odds ratio, corresponding Wald 95% CI, and p-value will be presented.

16.3.12 PROPORTION OF SUBJECTS, THE NUMBER OF DAYS, AND THE TOTAL NUMBER OF RESCUE MEDICATION**TABLETS USED DURING THE TREATMENT PHASE**

Proportion of subjects who used rescue medication at any time during the entire treatment period and descriptive statistics for the number of days these subjects used rescue medication and the total number of rescue medication tablets used during the treatment phase will be presented by treatment arm.

The number and percentage of subjects using rescue medication will be summarized by treatment and overall. A logit model will be used to compare treatment against placebo. This model will not contain any baseline covariates but will present an estimate of the odds ratio, Wald 95% confidence interval, and p-value for use of rescue medication. A by-subject listing of

Noven Pharmaceuticals, Inc.

Protocol HP-5000-US-07

Statistical Analysis Plan

Page 38 of 58

all efficacy assessments collected will be presented.

For number of days of rescue medication and number of tablets of rescue medication during the treatment phase, an independent two sample t-test will be used to compare treatment against placebo. An estimate of the difference, the 95% CI, and the p-value will be presented. If the normality assumption is not supported by the data, a Wilcoxon Rank Sum Test will be used.

16.3.13 THE ONSET OF THE EFFECT: PAIN INTENSITY ASSESSED ON AN 11-POINT NRS CHANGE FROM BASELINE

Onset of the effect of HP-5000 will be defined as the first significant difference in NRS pain reduction between HP-5000 vs Placebo.

16.3.14 MINI-OA KNEE AND HIP QOL (MINI-OAKHQOL) SCORES CHANGE FROM BASELINE AT WEEKS 4 AND 12

The Mini-OA Knee and Hip QOL (Mini-OAKHQOL) questionnaire contains 20 items that describes QOL in six domains: physical activities (item numbers 1, 2, 3, 4, 5, 7, and 11), mental health (item numbers 8, 9, 17, and 18), pain (item numbers 12, 13, and 16), social support (item numbers 19 and 20), social functioning (item numbers 14 and 15), and Independent Items (item 6 and 10). Each item is scored on a scale of 0 to 10. For each specific domain, a score is obtained by computing the mean of the items in that domain, for each subject at baseline and subsequent visits. The derived scores at baseline and post-baseline visits will be summarized as a change from baseline to the post-baseline visit. The baseline, post-baseline, and change from baseline will be tabulated for each domain, except for the Independent Items domain, by treatment group and overall.

Mini-OAKHQOL for each domain will be analyzed using MMRM with change from baseline as the repeated dependent variable, with effects for treatment (HP-5000 and placebo), visit, treatment-by-visit interaction, and the baseline score as the covariate. With no adjustment for intercurrent events.

16.3.15 WORK PRODUCTIVITY AND ACTIVITY IMPAIRMENT QUESTIONNAIRE FOR OSTEOARTHRITIS (WPAI: OA) IMPAIRMENT SCORES CHANGE FROM BASELINE AT WEEKS 4 AND 12

Work Productivity and Activity Impairment Questionnaire for Osteoarthritis (WPAI: OA) impairment scores change from baseline at Weeks 4 and 12 will be tabulated. The score for each of the domains (work time missed, impairment at work, overall work productivity loss, activity impairment) from the 6-item questionnaire (Q1 through Q6) will be used to analyze the

Noven Pharmaceuticals, Inc.

Protocol HP-5000-US-07

Statistical Analysis Plan

Page 39 of 58

four endpoints using the formulas below.

Endpoint	Formula
1.Percent Activity Impairment due to OA	$Q6*10$
2.Percent Impairment while working due to OA	$Q5*10$
3. Percent Overall Work Impairment due to OA	$100*\{Q2/(Q2+Q4) + [1-Q2/(Q2+Q4)]*(Q5/10)\}$
4.Percent work time missed due to OA	$100*Q2/(Q2+Q4)$

The sub-scores are expressed as an impairment percentage (range from 0 to 100), with higher numbers indicating greater impairment and less productivity.

Percent Activity Impairment for each endpoint will be analyzed using MMRM with change from baseline as the repeated dependent variable, with effects for treatment (HP-5000 and placebo), visit, treatment-by-visit interaction, and the baseline score as a covariate. With no adjustment for intercurrent events.

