## 9.11. Rescue Medication

If needed, subjects will be allowed to take up to a maximum of 2 g (4 × 500 mg tablets) of oral APAP per day (as provided by the Sponsor or designee) as rescue medication for the treatment of the target knee pain of OA because of lack of efficacy of study drug (not for the non-target knee) if the subject does not feel enough pain relief by the study drug and any other aches they might experience during the trial such as headache and reduction of fever except within 3 calendar days prior to the Baseline Visit, on the day of Baseline Visit (V3), from Baseline Visit until Visit 4, within 2 calendar days prior to all subsequent visits (V5, V6, V7, and V8), and on the day of the clinic visits (V4, V5, V6, V7, and V8). Information regarding the use of rescue medication, such as the number of tablets taken, the time when it was taken, and the reason of use, will be recorded on the eDiary. Subjects should not use OTC APAP as rescue medication, i.e., they should only use the APAP provided by the Sponsor or designee. Rescue medication will be labeled appropriately for the study to ensure visual difference from similar OTC medications and to ensure proper understanding the rescue medication should be used for this study. NSAIDs or any other analgesics except study drug and rescue medication provided will not be permitted from the time that informed consent form is signed until study completion or early termination. Stable low doses of ASA up to 81 mg/day will be allowed.

Subjects are **NOT** allowed to apply study treatment drug (HP-5000/Placebo) on the non-target knee at any time during the Double-blind Treatment Phase.

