#### **13.4.3.3 Analyses for Secondary Endpoints**

All WOMAC LK3.1 OA Indices, PGA, PGIC, and NRS secondary efficacy endpoints will be analyzed similar to the primary analyses. An MMRM model will be used with change from baseline as the repeated dependent variable, with treatment (HP-5000 and placebo), visit, treatment-by-visit interaction, and the baseline assessment score as covariates.

The observed value and change from baseline each assessment score will also be summarized descriptively by visit using summary statistics in addition to the above noted model.

The proportion of responders and non-responders for WOMAC pain, WOMAC physical function or users of rescue medication will be summarized by visit. Treatment comparisons will be made using a logit model with treatment effect as the only term in the model.

The pain intensity assessed on an 11-point NRS average and worst score between Baseline and each day will be tabulated by day and presented graphically.

A weekly average of all available pain scores will be calculated using the 11-point NRS average and worst score. MMRM model will be used to address the secondary objective to compare for change from baseline between treatment arms by weeks; and data will be presented graphically. The all available scores of daily NRS scores evaluated when the subjects replace the patch and the NRS scores evaluated before any rescue medication use will be analyzed.

The NRS pain score for assessment at Weeks 1, 2, 4, 8, and 12 is a mean of the NRS pain scores reported for pain over the last 24 hours for the 3 days (the last 2 days prior to each clinic visit and the day of the clinical visit) using the 11-point NRS average and worst score. MMRM model will be used to address the secondary objective to compare the change from baseline between treatment arms by weeks; and data will be presented graphically.

To address the objective for rescue medication, the proportion of subjects, the number of days using rescue and total rescue use during the entire treatment period will be summarized by treatment arms.

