3. STUDY DESIGN

3.1 GENERAL DESCRIPTION

This is a multicenter, randomized, double-blind, placebo-controlled Phase 3 study in the US

Noven Pharmaceuticals, Inc.

Protocol HP-5000-US-07

Statistical Analysis Plan

Page 14 of 58

evaluating the efficacy and safety of HP-5000 in subjects with OA pain of the knee.

The study will consist of up to a 28-day Screening Phase that will include a Washout Period of current prescription and over the counter (OTC) analgesics; a 12-week Double-blind Treatment Phase, and a 1-week safety Follow-up Phase.

Screening Phase: Subjects will be seen in the clinic where the study will be described to them and will be asked to sign the informed consent form (ICF). No screening procedures may begin prior to obtaining informed consent. After obtaining a written informed consent, subjects will be screened for participation in the study. The target knee for the purpose of the study will be defined as the one which causes the subject more pain than the other knee and will be identified at the Screening visit using the NRS score. During the Screening Phase, subjects will complete a daily electronic diary (eDiary) to record pain severity of their target knee. Subjects who satisfy the entry criteria will be instructed to begin the Washout Period for 7 to 14 days, or at least 5 half-lives, whichever is longer, prior to the Baseline Visit (Day 0).

During the Washout Period, current prescription and OTC analgesics will be discontinued. However, rescue medication (acetaminophen [APAP]) for the treatment of any other aches the subject might experience during the trial, such as headache, reduction of fever, and the target knee pain of OA (not for the non-target knee) will be permitted (a maximum of 2 g/day) except within 3 calendar days prior to the Baseline Visit (i.e., rescue medication is prohibited for 2 days until clinic visit on Day 0 and on the day of Baseline Visit [V3]). During the Washout Period, subjects will complete a daily eDiary to record rescue medication usage in addition to pain severity of their target knee. Following completion of the Washout Period, subjects will return to the clinic for their Baseline Visit (Day 0). Eligible subjects will be randomized to either HP-5000 or placebo in a 1:1 ratio.

Treatment Arm	Treatment
HP-5000	HP-5000 [REDACTED] patch Each patch contains [REDACTED] diclofenac sodium.
Placebo	HP-5000 [REDACTED] Placebo patch Each patch contains 0% [REDACTED] diclofenac sodium.

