Double-blind Treatment Phase: Subjects will apply a single patch to the target knee [REDACTED]

[REDACTED] After the removal of the patch [REDACTED], a new patch will be applied to a different site on the target knee. Subjects will be instructed to rotate the patch application site [REDACTED] to alternate sides (inner and outer) of the target knee. During the Double-blind Treatment Phase, subjects will also complete a daily eDiary to record patch application and removal time, adhesion, irritation, discomfort, and pain assessments; and

Noven Pharmaceuticals, Inc.

Protocol HP-5000-US-07

Statistical Analysis Plan

[figure not shown]
Page 15 of 58

amount of rescue medication (APAP) taken daily, if applicable. A maximum of 2 g/day of APAP will be allowed as rescue medication except from Baseline Visit until Visit 4, within 2 calendar days prior to all subsequent visits (V5, V6, V7, and V8), and on the day of the clinic visits (V4, V5, V6, V7, and V8).

NOTE: Subjects are NOT allowed to apply HP-5000 on the non-target knee at any time during the study.

Follow-up Phase: Subjects will have a safety visit approximately 7 days after the Week 12 End-of-Treatment Visit. The investigator or qualified study staff will contact all subjects by phone for continued safety monitoring of AEs. At the discretion of the investigator, subjects may have to return to the clinic for their Follow-up Visit.

Figure 1: A Schematic of the Study Design

Sample Size: Based on the HP-5000 Phase 2 study results, the assumed effect size of the test product in the pivotal study will be about [REDACTED]. The sample size of [REDACTED] subjects per treatment arm (or total of about [REDACTED] subjects) will be included in order to have 80% power to demonstrate statistically significant difference versus placebo using a 2-sided overall Type I Error rate of 0.05.

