6.4 STATISTICAL TESTS

Unless otherwise indicated, all testing of statistical significance will be 2-sided, and a difference resulting in a p-value of <0.05 will be considered statistically significant.

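### SAP 16.3.12 compares rescue use for all reasons together; adding the same comparisons for use recorded as target-knee pain would sharpen the endpoint at little cost

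*SAP*

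**What the plan says.** Protocol 9.11 gives the sponsor-supplied acetaminophen two purposes. One is target-knee osteoarthritis pain when the patch gives too little relief. The other is "any other aches they might experience during the trial such as headache and reduction of fever". The same section bars over-the-counter acetaminophen and, apart from stable low-dose aspirin, any other analgesic. A tablet taken for a headache therefore normally comes from the rescue supply.

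The reason is collected. Protocol 9.11 says that the number of tablets, "the time when it was taken, and the reason of use, will be recorded on the eDiary". The at-home procedures in Protocol 10.1.3 and footnote f of the Schedule of Events repeat this. Protocol 10.3.1.5 places the same information on the concomitant medication eCRF.

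Rescue use is listed among the secondary efficacy endpoints (Protocol 13.1.3, SAP 2.2.1). For its analysis, Protocol 13.4.3.3 says that "the proportion of subjects, the number of days using rescue and total rescue use during the entire treatment period will be summarized" by arm. SAP 16.3.12 takes "Proportion of subjects who used rescue medication at any time during the entire treatment period", compares it with a treatment-only logit model, and compares days and tablets with a t-test or, if normality fails, a Wilcoxon test. None of this is restricted or split by reason. SAP 14 only lists daily amounts by subject, and SAP 16.3.16 mentions only users of rescue medication.

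**The concern.** By the protocol's own description, knee-pain use signals that the patch is not working well enough. Use for a headache or a fever does not. If non-knee use is about equal in the two arms, it raises both arms' proportions of users and pulls the odds ratio towards 1. It does the same to days when both kinds of use fall on one day, and it adds noise to tablet counts. A real difference in knee-pain rescue could then be harder to see in an endpoint for which the SAP reports an estimate, a 95% confidence interval and a p-value, although the field needed to separate the two kinds of use is already collected.

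**Working it through.** **Inputs from the documents.** Allocation: "Eligible subjects will be randomized to either HP-5000 or placebo in a 1:1 ratio" (SAP 3.1). Significance: SAP 6.4 sets the general rule that "all testing of statistical significance will be 2-sided, and a difference resulting in a p-value of <0.05" counts as significant. Power: SAP 3.1 says the planned number per arm "will be included in order to have 80% power to demonstrate statistically significant difference versus placebo". The number per arm and the assumed effect size are redacted, and no rate or power is stated for rescue use, so there is no figure of the plan's own to reproduce. Every rate and sample size below is an assumption.

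**Users (yes/no).** Let k be the proportion using rescue for knee pain and o the proportion using it for other reasons, with o equal in both arms and independent of k. Then any use = 1 − (1 − k)(1 − o), and the risk difference shrinks by the factor (1 − o).

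Assume k = 0.30 on HP-5000 and 0.45 on placebo. Knee-pain odds ratio = (0.30/0.70)/(0.45/0.55) = 0.524. Relative information is (ln OR)² / [1/(p₁q₁) + 1/(p₂q₂)], with q = 1 − p, divided by its knee-only value.

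| o | Any use, HP-5000 | Any use, placebo | Difference (points) | Odds ratio | Relative information |
|---|---|---|---|---|---|
| 0 | 0.30 | 0.45 | 15 | 0.524 | 1.00 |
| 0.2 | 1 − 0.70×0.80 = 0.44 | 1 − 0.55×0.80 = 0.56 | 12 | 0.617 | 0.60 |
| 0.4 | 1 − 0.70×0.60 = 0.58 | 1 − 0.55×0.60 = 0.67 | 9 | 0.680 | 0.36 |
| 0.6 | 1 − 0.70×0.40 = 0.72 | 1 − 0.55×0.40 = 0.78 | 6 | 0.725 | 0.20 |

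A second assumed case, k = 0.40 against 0.50, shows the same pattern. As o goes from 0 to 0.1, 0.2, 0.3, 0.4 and 0.5, the odds ratio moves from 0.667 to 0.697, 0.722, 0.744, 0.762 and 0.778. At an assumed 250 per arm, power falls from 61% to 52%, 44%, 36%, 30% and 24%.

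**Days.** A day with both kinds of use counts once, so overlap shrinks the difference in the same way. Where the two kinds of use fall on different days, only noise is added.

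**Tablets.** If the two kinds of use add and are uncorrelated, and the daily maximum is ignored, the mean difference is unchanged. The SD grows by √(1 + r²), where r is the SD of non-knee tablets divided by the SD of knee tablets. An assumed standardized effect of 0.25 becomes 0.243, 0.224, 0.200 and 0.177 for r = 0.25, 0.5, 0.75 and 1. Power at 250 per arm falls from 79.8% to 77.4%, 70.5%, 60.9% and 50.7%.

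**The case against.** The strongest reply is that the SAP analyses exactly what the protocol defines. The objective is the pattern of rescue use, the endpoint is total use, and rescue medication itself is defined to include other aches and fever. This stands. A reader might infer that the endpoint is misdefined, or that a knee-pain variable should replace it; the documents support neither, because no knee-pain rescue endpoint is defined anywhere. Replacement would also depart from the protocol, while SAP 3.3 declares no changes from it.

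A reader might also infer that one tablet for a cold weighs the same as daily tablets for patch failure. That is true only of the yes/no measure. SAP 16.3.12 also compares days and tablets, which separate the two subjects, and restricting by reason would not cure the yes/no measure of this. Nor does either document say that all-reason use will be presented as a measure of knee pain.

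The size is open to challenge too. The rates are assumed, and so is independence. If subjects who take acetaminophen for headache also tend to take it for the knee, what matters is other-reason use among those who do not use it for the knee. That is then lower than the overall rate, so the loss is smaller than in the table. The endpoint also lies outside the fixed-sequence procedure. Finally, SAP 8 leaves table content to shells that are not among the documents; they might contain a split by reason. The SAP text, which specifies the comparisons, does not.

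**Conclusion.** This is a cheap improvement, not the correction of an error. The all-reason comparisons are legitimate and should stay. For efficacy they are a blunter instrument than the collected data allow: diluted for users and for overlapping days, and less precise for tablets. This holds if non-knee use is similar in the two arms; if it differed, the all-reason contrast would be biased as a measure of knee-pain rescue rather than only diluted. The direction follows from the definitions. The amount cannot be derived from the documents, and the range of 0.617 to 0.725 against 0.524 is an illustration for the yes/no measure only. No error-controlled conclusion depends on this endpoint.

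**What to change.** In SAP 16.3.12, keep the protocol-defined all-reason comparisons of users, days and tablets. Before unblinding, pre-specify the same three comparisons restricted to use recorded for target-knee pain, and show other-reason use descriptively in the same table.

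State how the recorded reason maps to target-knee pain, and give a rule for missing, multiple or free-text reasons. One option is to count such use as knee-pain use, with the all-reason result as the check. Name the source, since Protocol 9.11 points to the eDiary and 10.3.1.5 to the concomitant medication eCRF. Record the added comparisons in SAP 3.3.

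The 24-hour intercurrent-event rule for WOMAC and the rescue rules stay as they are. The cost is a few sentences and table rows, some coding work if reasons are free text, and reliance on the reason the subject states while blinded. Timing matters: a split by reason chosen after unblinding would be post hoc.

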**10.1.1.2 Washout Visit (Visit 2)**

The following procedures will be performed at the Washout Visit (V2):

1. Confirm subject's continued eligibility relative to inclusion/exclusion criteria.
2. Review eDiary NRS 11-point pain scores.   

██████████ will be entered to the eCOA system and the mean NRS scores will be calculated.

3. Record the eligibility of the subject in IWRS. If the subject screen fail, the date and the reason will be recorded in IWRS.
4. Placebo training will be performed to educate subjects. The aim is to minimize the placebo response and increase their awareness for the purpose of the trial to determine a new drug is effective and safe.
5. Subjects whose eligibility has been preliminarily confirmed will be asked to washout of their current medications for at least 7 days to a maximum of 14 days (or at least 5 half-lives, whichever is longer).
6. Subjects will be instructed by the site to stop taking all prescription and physician recommended OTC analgesic medications, but will be informed that rescue medication (i.e., APAP) may be used (a maximum of 2 g/day) as needed except **within 3 calendar days prior to the Baseline Visit (V3) and the day of Baseline Visit (V3)**.
7. Dispense rescue medication.
8. Ensure that the subjects have access to, and understands how to access and use, the eDiary.
9. Instruct the subject to continue to assess and record their target knee pain at home daily, using the NRS 11-point pain scale in the eDiary during the Washout Period.
10. Subjects will be instructed to record the number of tablets of rescue medication used, the time and the reason in the eDiary.

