16.3 OTHER SECONDARY EFFICACY

Other secondary efficacy analyses will be performed for the ITT Set. For each below secondary efficacy variable, tables will be produced that display descriptive and inferential statistics by visit and treatment group. For continuous change from baseline variables descriptive and inferential statistics, comparable to those described in [section 16.1.3](#) for the primary efficacy variable will be presented. With no adjustment for intercurrent events.

For the secondary variables expressed as proportion of subjects with a response that is categorized as binary a logistic regression model will be used to obtain the point estimate of the odds ratio between treatment groups (HP-5000 and placebo) and the associated 95% confidence interval.

16.3.1 WOMAC LK3.1 OA (PAIN) CHANGE FROM BASELINE AT WEEKS 1, 2, 4, AND 8

The change from baseline will be analyzed using a MMRM analysis. As described in [section](#)

Noven Pharmaceuticals, Inc.
Protocol HP-5000-US-07

[16.1.3](#) for the WOMAC pain score, the same MMRM model will be applied.

A plot of the LS Mean change from baseline by visit will be presented.

16.3.2 WOMAC LK3.1 OA (PHYSICAL FUNCTION) CHANGE FROM BASELINE AT WEEKS 1, 2, 4, AND 8

The change from baseline will be analyzed using a MMRM analysis. As described in [section 16.1.3](#) for the WOMAC physical function score, the same MMRM model will be applied.

A plot of the LS Mean change from baseline by visit will be presented.

16.3.3 WOMAC LK3.1 OA (STIFFNESS) CHANGE FROM BASELINE AT WEEKS 1, 2, 4, AND 8

The change from baseline will be analyzed using a MMRM analysis. As described in [section 16.1.3](#) for the WOMAC stiffness score, the same MMRM model will be applied.

A plot of the LS Mean change from baseline by visit will be presented.

16.3.4 WOMAC LK3.1 OA (COMPOSITE SCORE) CHANGE FROM BASELINE AT WEEKS 1, 2, 4, AND 8

The change from baseline will be analyzed using a MMRM analysis. As described in [section 16.1.3](#) for the WOMAC composite score, the same MMRM model will be applied, with no adjustment for intercurrent events. The WOMAC Composite score is calculated by finding the total of the scores for the 3 subscales, WOMAC pain, WOMAC physical function and WOMAC stiffness, and then dividing by 96. Higher scores on the WOMAC indicate worse pain, stiffness, and functional limitations.

16.3.5 CHANGE FROM BASELINE IN PAIN INTENSITY ASSESSED ON AN 11-POINT NRS AT WEEKS 1, 2, 4, 8, AND 12

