All available scores of daily NRS scores evaluated when the subjects replace the patch and the NRS scores evaluated before any rescue medication use will be included. Weekly pain would be the mean of average NRS pain and mean of worst NRS pain over 7 days (e.g., Week 1 = average pain scores on Days 1 through 7). Baseline is defined 

A weekly average of all available daily pain scores will be calculated from subject's diaries. MMRM model will be used with change from baseline as the repeated variable, with effects for treatment (HP-5000 and placebo), visit, treatment-by-visit interaction, and the baseline 3-day average NRS score as a covariate. With no adjustment for intercurrent events.

A figure plotting the weekly average of the average and worst NRS pain scores by week will be generated.

Noven Pharmaceuticals, Inc.

Protocol HP-5000-US-07

16.3.7 CHANGE FROM BASELINE IN PATIENT GLOBAL ASSESSMENT (PGA) AT WEEKS 1, 2, 4, 8, AND 12

Subject's will be asked to complete the following statement: "How would you rate your osteoarthritis condition over the last 24 hours?" using a 5-point scale from 0 (Very Good) to 4 (Very Poor).

Change from baseline in PGA at Weeks 1, 2, 4, 8, and 12 (visits 4, 5, 6, 7, and 8) will be analyzed similar to the primary analyses (refer to [section 16.1.3](#)). An MMRM model will be used with change from baseline in PGA as the repeated dependent variable, with effects for treatment (HP-5000 and placebo), visit, treatment-by-visit interaction, and the baseline PGA score as a covariate. With no adjustment for intercurrent events. The observed value and change from baseline will also be summarized descriptively by visit using summary statistics in addition to the above noted model.

The responders are defined as subjects achieving a score of

0: Very Good or

1: Good

Non-responders are defined as subjects achieving a score of

2: Moderate or

3: Poor or

4: Very Poor

[figure not shown]
Subjects not assessed will be considered as having missing data.

The proportion of PGA responders and non-responders will be summarized by visit. Treatment comparisons will be made using a logit model adding PGA baseline as the covariate. This model will present an estimate of the odds ratio, Wald 95% CI, and p-value. The sample SAS code used for the Logit model for the PGA analysis can be found in [Appendix 2](#).

16.3.8 PATIENT GLOBAL IMPRESSION OF CHANGE (PGIC) AT WEEKS 1, 2, 4, 8, AND 12

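### The rescue comparisons leave out pre-randomisation rescue use and pain that are already recorded, and rescue days are described among users only

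*SAP*

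**What the plan says.** SAP 16.3.12 has three parts.

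- **Any rescue use.** A logit compares the arms and reports an odds ratio with a Wald interval and p-value: "This model will not contain any baseline covariates".
- **Days and tablets.** "For number of days of rescue medication and number of tablets of rescue medication during the treatment phase, an independent two sample t-test will be" the means of comparing active with placebo, and a Wilcoxon rank sum test replaces it if normality is not supported.
- **Description.** The section gives the proportion who used rescue and "descriptive statistics for the number of days these subjects used rescue medication". The days summary is therefore limited to users.

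SAP 16.3 opens with "Other secondary efficacy analyses will be performed for the ITT Set", and SAP 5.1 defines that set as everyone consented and randomised. No sentence says that non-users count as 0, or how early withdrawals count.

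Protocol 13.4.3.3 covers users of rescue by name: "Treatment comparisons will be made using a logit model with treatment effect as the only term in the model". It summarises days and total use by arm, with no limit to users, and plans no test of them; the t-test is a SAP addition. SAP 3.3 lists no changes from the protocol. Protocol 13.4.3.2 keeps this endpoint outside the fixed sequence.

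Both candidate baselines exist before randomisation. At the Washout Visit (Protocol 10.1.1.2): "Subjects will be instructed to record the number of tablets of rescue medication used, the time and the reason in the eDiary". Target-knee NRS pain is recorded daily through washout, and SAP 16.3.5 and 16.3.6 already use a baseline NRS score as a covariate. For the PGA responder model, SAP 16.3.7 says: "Treatment comparisons will be made using a logit model adding PGA baseline as the covariate".

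**The concern.** Rescue use is a listed secondary efficacy endpoint. A subject who needed many tablets in washout, or who entered with more pain, may well need more rescue on treatment. If so, an unadjusted comparison leaves explainable variation in the error term although the data to remove it are already in the diary.

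The users-only days summary raises a different matter. Being a user is determined after randomisation. If treatment works partly by keeping subjects off rescue, the remaining users in the two arms are no longer comparable, and their mean days can show no difference or one in the wrong direction.

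**Working it through.** **1. The plan's own figure.** The only power figure is 80% at two-sided 0.05 (SAP 3.1, Protocol 13.2). Its effect size and sample size are blacked out, so it cannot be reproduced; that is no fault of the plan. With n per arm = 2(1.960 + 0.842)²/d², assumed standardised effects d of 0.20, 0.30 and 0.50 give 393, 175 and 63. No power is stated for rescue, so every rate, size and correlation below is an assumption.

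**2. Logit for any use.** The model is logit P(use) = a(arm) + βx, with x a standard normal baseline covariate. Placebo use is 60%. Active use is set for about 80% unadjusted power: 43.9%, 47.5% and 50.2% at 150, 250 and 400 per arm. There were 3,000 simulated trials per cell, so the simulation error is √(0.8 × 0.2/3000) = 0.7 points. Power in %, unadjusted → adjusted:

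| β (odds ratio per SD) | 150/arm | 250/arm | 400/arm |
|---|---|---|---|
| 0 (1.00) | 79.5 → 79.4 | 80.8 → 80.0 | 81.2 → 81.2 |
| 0.5 (1.65) | 79.2 → 82.2 | 80.3 → 81.4 | 80.0 → 82.5 |
| 1.0 (2.72) | 80.8 → 87.5 | 80.6 → 86.8 | 80.3 → 86.3 |
| 1.5 (4.48) | 79.7 → 90.8 | 80.0 → 90.4 | 81.9 → 91.7 |

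The largest gain is 90.8 − 79.7 = 11.1 points. Type I error was 4.4% to 5.5% with and without the covariate.

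A second set-up holds the conditional log odds ratio at −0.5 (250 per arm, 2,500 trials). For β = 0.5, 1.0 and 1.5, power goes from 74.8 to 76.9, 65.8 to 72.0 and 52.0 to 63.9: gains of 2.1, 6.2 and 11.9 points. A repeat with intercept 0.25 gave 77 to 78, 65 to 71 and 52 to 66. The top of the range is thus roughly 12 points, and only for a very strong covariate.

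**3. Days and tablets.** ANCOVA multiplies the residual variance by 1 − ρ², where ρ is the correlation between baseline and outcome. Power = Φ(d√(n/2)/√(1 − ρ²) − 1.96). With d = 0.30 and n = 175, 0.30 × √87.5 = 2.806. At ρ = 0.5 this gives 2.806/0.866 − 1.96 = 1.28, so power is 90%. For ρ = 0.2, 0.3, 0.4, 0.5 and 0.6, power rises from 80% to 81.7, 83.7, 86.5, 90.0 and 93.9%. Rescue counts will be skewed with many zeros, so this is only a guide.

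**4. Users only against all randomised.** If 60% and 40% use rescue for 10 days each, the means per randomised subject are 0.60 × 10 = 6 and 0.40 × 10 = 4 days, but the difference among users is 0. In simulation at 250 per arm:

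- Use falls from 60% to 47.5%, with users averaging 15 days in both arms: −1.89 days over all randomised (0.475 × 15 − 0.60 × 15 = −1.88), and −0.02 among users.
- Treatment removes the lighter users: −1.24 over all randomised, but +1.76 among users.

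**5. Observation time.** Protocol 9.11 bars rescue from Baseline until Visit 4, on each visit day, and for 2 calendar days before Visits 5 to 8. With visits on target days, Days 8 to 84 are 77 days, less 4 × 3 = 12, which leaves 65 permitted days. A subject leaving just after Visit 6 has 21 − 2 × 3 = 15; one leaving before Visit 4 has 0. At one tablet per permitted day the totals would be 65, 15 and 0. Raw counts therefore reward early withdrawal.

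**The case against.** The strongest reply is that nothing here is wrong. The SAP's rescue logit is the protocol's own model, its type I error is nominal, and treatment-only logits are the SAP's usual choice (PGIC and the WOMAC responders). The PGA model is a weak precedent, because PGA has a baseline on the same scale and the protocol's treatment-only sentence does not name it. All of this stands, so the loss is efficiency only.

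Prediction from washout may also be weak. Washout lasts 7 to 14 days, rescue is barred just before Baseline, it may be taken for headache or fever, and entry criteria based on NRS pain probably narrow its range. This stands too, and it is why the range starts at 0.

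A reader might infer that the days and tablets test is run on users only and so leaves the randomised comparison. The documents do not support that. The restriction sits in the descriptive sentence alone, the test paragraph has none, and SAP 16.3 places these analyses in the ITT set. Nor would an effect on any use be hidden, since the same section reports and tests that proportion. What remains is that diary rescue entries are made only when rescue is taken and no rule sets non-users to 0, so a programmer could leave them missing.

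Simply counting non-users as 0 also has a flaw: as step 5 shows, a subject who leaves before Visit 4 would score the best possible result.

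**Conclusion.** A worthwhile refinement of low consequence. The rescue analyses are valid as written, and the logit follows the protocol. They give up precision if washout rescue use or baseline pain predicts later use: about 0 to 12 power points for the logit over covariate odds ratios of 1 to 4.5 per SD, and about 2 to 14 for days at correlations of 0.2 to 0.6. These figures rest on assumed sample sizes, rates and prognostic strengths that the documents do not give. A covariate that predicts nothing costs almost nothing.

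The users-only restriction is established for the descriptive days summary, where it is narrower than the protocol's summary by arm. It is not established for the t-test. The handling of non-users and early withdrawals is unstated. The endpoint is outside the fixed sequence, so no confirmatory claim depends on it.

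**What to change.** Amend SAP 16.3.12 before unblinding:

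- Add mean rescue tablets per permitted washout day and baseline NRS average pain to the logit. Use ANCOVA, or its rank version, with the same covariates for days and tablets.
- Label the adjusted odds ratio as conditional on baseline, keep the unadjusted result as supportive, and record the departure from Protocol 13.4.3.3 in SAP 3.3.
- Include all ITT subjects with non-users at 0, and express days and tablets per permitted observed treatment day. State the rule for a subject with no permitted day (the ratio is undefined), for tablets taken on barred days, and for days without a diary entry.
- Show an all-randomised summary of days and tablets by arm beside the users-only one.

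The washout denominator needs one definition of the barred window. Protocol 7.1 explains it as 2 days plus the visit day, while 9.11 lists 3 calendar days and the visit day; these passages must be reconciled.

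The cost is SAP wording, one derived covariate from existing diary data and a few extra table rows. The downside is that the conditional odds ratio is a different quantity from the unadjusted one.
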